### **7.5.8 Progression-free Survival**

Progression-free (PFS) survival was not described in the study protocol and was added in this SAP. PFS is defined as the number of days from the date of randomization to the date of disease progression (including relapse) or death from any cause, whichever occurs first. In the absence of disease progression or death at the time of analysis, PFS time will be censored on the last date the subject is known alive. The Kaplan-Meier plot will be provided based on the Efficacy Analysis Set. Estimated median survival time (days) and 95% CIs will also be provided if available.

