- Hematology: Collect weekly through Cycle 2, at Days 1 and 15 in Cycles ≥3, and at treatment discontinuation. Hematology done during Screening within 1 week before the start of study treatment does not need to be repeated on Cycle 1 Day 1. Complete blood count and differential, with specific output being hemoglobin, platelet count, white blood cell count and percent neutrophils (percent polymorphonuclear neutrophils and bands) or an absolute neutrophil count, and percentage of blasts. Additional laboratory assessments may be done at the investigator's discretion for clinical intervention.
- Chemistry: At Screening, predose on Day 1 of Cycles ≥2, and at treatment discontinuation. Must include glucose, calcium, magnesium, albumin, total protein, sodium, potassium, CO2, chloride, BUN, creatinine, lactate dehydrogenase, alkaline phosphatase, ALT, AST, total bilirubin, direct bilirubin only if total bilirubin is elevated above the protocol inclusion criterion. Additional laboratory assessments may be done at the investigator's discretion for clinical interventions.
- Urinalysis: At Screening, predose on Day 1 of Cycles ≥2, and at treatment discontinuation. Dipstick only (microscopic analysis required only to follow up abnormal findings or if dipstick not performed). See Table 10.
- Pregnancy test: At Screening and at treatment discontinuation. Serum or urine; only for women of child-bearing potential.
- LINE-1 demethylation: Obtain whole blood sample predose on Day 1 of Cycles 1 and 2 (as baseline), Days 8, 15, 22 of Cycles 1 and 2; and Day 1 of Cycle 3.

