- Bone marrow aspirate or biopsy: At Screening or within 21 days before Cycle 1 Day 1; on or before Day 1 of Cycles 3, 5, 7, and then every 3 months in first year and every 6 months thereafter. Bone marrow aspirate or biopsy differential will be performed according to local standard practice. A bone marrow biopsy can be done if no aspirate is available. A manual differential of the myeloid cells in bone marrow will be performed with a minimum of 100 cells counted and a specific myeloblast percent generated. Bone marrow aspirate or biopsy differential may include the following: total cells counted, metamyelocytes, lymphocytes, normoblasts, myeloid and erythroid maturation, blasts, segmented neutrophils, plasma cells, megakaryocytes, presence of dysplasia, promyelocytes, eosinophils, monocytes, M:E ratio, cellularity: % cellularity; hypocellular, hypercellular, normocellular; myelocytes, basophils, pronormoblasts, and other. An anonymized report of all bone marrow testing results will be recorded on the electronic Case Report Form. A portion of bone marrow aspirates will be used for assessing disease-associated gene mutations. Cytogenetics will be reviewed on the screening bone marrow and should include at least 20 clones. If cytogenetics are abnormal, they must be reviewed again in subsequent bone marrow aspirates or biopsies.

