#### 9.5.6 Survival/Conversion to AML

Follow all subjects for survival/conversion to AML who have stopped study treatment. Contact subject every 3 months until death or withdrawal of consent or the close of the trial. This assessment may be conducted by telephone.

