#### 11.7.3 Leukemia-Free Survival

The number of days from randomization to the date when bone marrow or peripheral blood blasts reach  $\geq$ 20%, or death from any cause, will be measured for subjects in the Efficacy Analysis Set. Subjects who do not have events in leukemia-free survival will be censored on the last date of bone marrow or peripheral blood blasts assessment, whichever is later. Subjects who have bone marrow or peripheral blood blasts  $\geq$ 20% at baseline will be censored at the date of randomization. Leukemia-free survival will be presented using a Kaplan-Meier estimate. The 95% CI for the median of leukemia-free survival will be provided using the Kaplan-Meier procedure.

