### 7.5.1 Response Rate

The evaluation of response (Table 2) will be based on Modified IWG 2003 AML Response Criteria (Cheson et al 2003), and include CRp according to the DACO-016 study (Kantarjian et al 2012) for that CRp is not any response category of IWG 2003 AML Response Criteria (Cheson et al 2003). Subjects who do not have a valid post-treatment efficacy assessment (ie, no post-treatment BM/PB sample or the quality of BM/PB sample is not adequate for an assessment of efficacy) will be classified as not evaluable (NE) for response classifications. Subjects who cannot be classified into a response category (CR, CRi, or PR) or into the NE category will be classified as non-responders (NR). According to the recommendations of the European LeukemiaNet (Döhner et al 2017), progressive disease is defined as >50% increase in marrow blast % from baseline (15% increase in cases with <30% marrow blasts at baseline); or >70% marrow blasts over at least 3 months; or >50% increase in peripheral blasts to  $\geq 25 \times 10^9/L$  ( $\geq 25,000/\mu L$ ); and stable disease is defined as absence of CR, CR subtype, PR and progressive disease for at least 3 months. CRh, CR with partial hematologic recovery, is defined as <5% of blasts in the bone marrow, no evidence of disease, and partial recovery of peripheral blood counts (platelets  $>50,000/\mu L$  and ANC  $>500/\mu L$ ) (Kantarjian et al 2017). Evaluation of response will be conducted by Astex medical monitors assisted by programmed data listings, as detailed in the Astex AML Response Assessment Criteria (Section 8.1).

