### 7.5.5 Overall Survival

Overall survival (OS) is defined as the number of days from the date the subject was randomized to the date of death (regardless of cause). In the absence of documented death at the time of analysis, the OS time will be censored on the last date the subject is known alive.

The Kaplan-Meier plot will be provided based on the Efficacy Analysis Set. The median (and quartiles) duration of OS and the associated 95% CI will be estimated using the Kaplan-Meier method and the log-log transformation for the survival function. In addition, subject follow-up time in days will also be summarized.

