### **7.5.7 Event-Free Survival**

Event-free survival (EFS) was not described in the study protocol and was added in this SAP. EFS is defined as the number of days from the date of randomization to the date of treatment failure (disease progression/relapse, discontinue treatment due to disease progression or treatment-related adverse event, or alternative anti-leukemia therapy except for HCT) or death from any cause, whichever occurs first. In the absence of any of these events at the time of analysis, EFS time will be censored on the last date the subject is known alive. Subjects who do not have post-baseline information will be censored at the date of randomization. The Kaplan-Meier plot will be provided based on the Efficacy Analysis Set. Estimated median survival time (days) and 95% CIs will also be provided if available.

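### AML progression-free survival is censored at the last date known alive, so time after the last disease assessment counts as progression-free

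*SAP*

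**What the plan says.** SAP 7.5.8 counts progression (including relapse) or death as a PFS event. Without either, "PFS time will be censored on the last date the subject is known alive". SAP 7.5.5 uses the same date for survival: "the OS time will be censored on the last date the subject is known alive".

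Neighbouring rules differ:

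- **Event-free survival (SAP 7.5.7)** also uses last known alive but adds "Subjects who do not have post-baseline information will be censored at the date of randomization". PFS has no such clause.
- **Duration of CR/CRh (SAP 7.5.3)** is censored at the last marrow, blood or follow-up visit at which no event was seen.
- **Leukemia-free survival (Protocol 11.7.3, MDS/CMML)**: subjects without an event "will be censored on the last date of bone marrow or peripheral blood blasts assessment, whichever is later".

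The only visit schedule available is in the US MDS/CMML protocol. The Table 9 footnotes place marrow at screening and then "on or before Day 1 of Cycles 3, 5, 7, and then every 3 months in first year and every 6 months thereafter". For hematology they say "Collect weekly through Cycle 2, at Days 1 and 15 in Cycles ≥3, and at treatment discontinuation". After treatment stops, Protocol 9.5.6 says "Contact subject every 3 months until death or withdrawal of consent or the close of the trial. This assessment may be conducted by telephone".

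**The concern.** For survival, a contact showing that the subject is alive proves that no event has happened. For PFS it does not: SAP 7.5.1 defines progression by marrow or blood blasts, so it is mainly seen when someone looks. A subject who is no longer assessed stays in the Kaplan-Meier risk set while unable to have a blast-defined progression recorded. The denominator is too large, the estimated event rate too low, and the curve too high. The extreme case is the group described in SAP 7.5.1 as "Subjects who do not have a valid post-treatment efficacy assessment". Unless clinical progression or death is recorded, such a subject is progression-free for as long as anyone knows the subject is alive.

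At stake is a PFS curve, median and confidence interval in the analysis prepared for submission (SAP 6.0), with an error in the favourable direction.

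**Working it through.** **1. There is no figure in the plan to reproduce.** Neither document gives an expected PFS median, event count or precision. The finding rests on the wording: the censoring dates in 7.5.5 and 7.5.8 are identical.

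**2. One subject (dates assumed).** Treatment stops after three 28-day cycles without progression. 3 × 28 = 84, so discontinuation-visit hematology is placed on day 85.

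- Last known alive on day 183: 183 − 85 = 98 days counted as progression-free with no scheduled disease assessment.
- Last known alive on day 730: 730 − 85 = 645 days, and 645/730 = 88% of the subject's PFS time.

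**3. Illustration of direction.** Kaplan-Meier on 200,000 simulated subjects per setting. From the US protocol (assumed to hold for AML): marrow on days 57, 113 and 169 (Day 1 of Cycles 3, 5 and 7), then every 91 days in year 1 and every 183 days after. Other assumptions:

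- exponential PFS with median 4, 6 or 8 months; 35% of events are deaths without progression;
- mean survival after progression 4 or 8 months;
- follow-up uniform from 6 to 30 months;
- assessment stops at 0, 0.012, 0.027 or 0.07 per month;
- last contact 0 to 3 months before cut-off once assessment has stopped;
- progression is dated at the next scheduled marrow, and deaths always count.

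The reference is the same schedule with no stopping. With a true median of 6 months it gives 6.6 to 6.8 months and 26% at 12 months. Ranges cover the two post-progression survival assumptions.

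| Subjects whose assessment stops early | SAP rule: median (months) | SAP rule: 12-month PFS |
|---|---|---|
| 0% | as reference | as reference |
| 8% | 6.8–7.0 | 27% |
| 17% | 7.0–7.4 | 28–29% |
| 35% | 7.4–8.1 | 30–33% |

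Last-assessment censoring gives 6.5 to 6.7 months and 23% to 25%.

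| True median | Reference | SAP rule, some stopping | Last assessment, some stopping |
|---|---|---|---|
| 4 months | 4.4–4.6; 13% | 4.6–5.5; 14–20% | 4.5–4.9; 13–14% |
| 8 months | 8.5; 36% | 8.5–10.1; 37–43% | 8.5; 32–35% |

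Over all settings with some stopping, the SAP rule differs from the reference by 0 to +1.5 months and +0.8 to +7 points at 12 months. Last-assessment censoring differs by −0.1 to +0.4 months and −4.5 to +1.3 points. I re-ran the simulation and it agrees to within about 0.1 month.

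**4. Progression threshold (separate, smaller point).** The ELN 2017 column in SAP 8.1 requires a rise of at least 15 percentage points when baseline marrow blasts are below 30%. SAP 7.5.1 and Appendix C (Programming Guidelines) give 15% without saying points, and only Appendix C calls it a minimum. Read as points, nothing changes. Read as a relative change, the thresholds for baseline *b* below 30% are:

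| Baseline | 7.5.1: 1.15*b* | Appendix C: above 1.5*b* | ELN column: max(1.5*b*, *b* + 15) |
|---|---|---|---|
| 20% | 23% | 30% | 35% |
| 25% | 28.75% | 37.5% | 40% |
| 29% | 33.35% | 43.5% | 44% |

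At 30% or more all three agree.

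**5. Whether progression is assessed at all.** The study-specific cells for stable and progressive disease in SAP 8.1 say neither is assessed in this study. SAP 7.5.1, Appendix C and the response table shell define or report both, and 7.5.8 needs progression dates.

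**The case against.** The bias exists only if contact outlasts assessment, and the AML amendments that would settle this were not supplied. Protocol 9.5.6 covers conversion to AML as well as survival, and SAP 7.5.3 lists long-term follow-up visits as points where remission status is known, so follow-up may not be blind to disease. Clinical or symptomatic progression also counts as progression. These points stand as limits on size. They do not rescue the rule, because 7.5.8 requires only that the subject be alive, not that disease status was recorded.

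The event-free survival clause is a weak contrast, since post-baseline information is undefined there, and leukemia-free survival concerns another population. Both are fair; the case does not depend on either.

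The larger effects need heavy stopping: +1.5 months requires about 40% of subjects to stop assessment. The 12-month rate is not a stated output of 7.5.8, though it can be read from the planned curve. The 645-day example is deliberately extreme.

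Last-assessment censoring is not uniformly better. With no stopping it lowers 12-month PFS by 0.5 to 0.8 points where the current rule is unbiased. With a true median of 8 months and mean post-progression survival of 4 months, it lies further from the reference at 12 months at each stopping level (−1.4, −2.2 and −4.4 points against +1.0, +1.9 and +3.7). This stands, and is why both rules should be reported.

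The threshold and not-assessed wording looks like leftover drafting, and medical monitors adjudicate progression. That makes it minor, but it still needs reconciling.

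**Conclusion.** The concern holds. SAP 7.5.8 gives PFS the survival censoring date, so unassessed time is counted as progression-free. The wording is certain; the size is not. The bias is nil if disease assessment continues through follow-up, and upward if it stops before vital-status contact does. In the illustration the median rises by 0 to 1.5 months, resting on an MDS/CMML marrow schedule and assumed event and stopping rates.

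PFS is a descriptive secondary endpoint added in the SAP. The primary pharmacokinetic conclusion and the CR, CRi and PR rates are unaffected. The change should be made, but the trial's main conclusion does not hang on it. The 15% wording matters only if it is applied as a relative change.

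**What to change.** In SAP 7.5.8, censor subjects without progression or death at the latest of the last marrow assessment, the last peripheral blood blast assessment and the last documented investigator assessment of disease status. Censor at randomization if there is none after baseline. If AML follow-up contacts record disease status, those dates qualify and no information is lost. Keep last known alive as a sensitivity analysis. Consider the same date for event-free survival (7.5.7), which is less exposed because several of its events need no blast assessment.

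Separately, bring 7.5.1 and Appendix C into line with the SAP's own ELN column by stating that the 15% is in percentage points and is a minimum. Reconcile the cells that say stable and progressive disease are not assessed with 7.5.1, Appendix C, the table shell and 7.5.8.

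The cost is SAP wording and minor reprogramming, largely with assessment dates the response evaluation already needs. Reported PFS may look slightly less favourable.

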## **7.6 Safety Variables and Analyses**

Safety Analysis will be performed using the Safety Analysis Set (Section 5.4). Safety is assessed by subject-reported and investigator-observed adverse events (AEs), along with physical examination, clinical laboratory tests (hematology, chemistries and urinalysis), vital signs, concomitant medications, ECOG performance status and ECGs. Exposure to study treatment, deaths, and causes of deaths will be tabulated.

### **7.6.1 Study Treatment and Exposure**

The number of cycles completed or partially completed per subject will be summarized using descriptive statistics. Frequency count and percentage of dose delayed cycles and dose reduced cycles reported by the investigator will be summarized at the subject level and cycle level.

## 7.6.2 Adverse Events

Adverse events reported by study subjects or observed by investigators will be mapped to the appropriate System Organ Class (SOC) and Preferred Term (PT) according to the Medical Dictionary for Regulatory Activities (MedDRA). Severity of AEs will be graded using Common Terminology Criteria for Adverse Events (CTCAE) version 4.03.

Treatment-emergent AEs (TEAEs) are defined as events that first occurred or worsened on or after the date of the first dose of study treatment until 30 days after the last dose of study treatment or until the start of a post-treatment alternative anti-leukemia treatment, whichever occurs first, with the following exceptions: events that occurred after 30 days beyond the last dose of study treatment or the start of a post-treatment alternative anti-leukemia treatment will also be considered treatment-emergent if the events are both serious and related to the study treatment. For the purpose of determining whether an AE is a treatment-emergent AE, incomplete AE start and stop dates will be imputed conservatively following the data programming conventions as detailed in the Astex Data Programming Standards.

All AE data collected in the study database with an AE start date on or before the data cutoff date will be included in the data listings, including those that are not treatment emergent. Only TEAEs will be included in the AE summary tables.

An overall safety summary table containing counts and percentages of subjects with any AE, any AE Grade  $\geq 3$ , AE leading to treatment discontinuation, any SAE, and subcategories of SAEs (death vs not death) will be produced.

Related events are those that the Investigator considered to be related to study treatment as described in the study protocol. All summaries of AEs will be made separately in the following groups:

- IV decitabine in Cycle 1 or Cycle 2.
- ASTX727 in Cycle 1 or Cycle 2.
- ASTX727 in Cycle 3 or later.
- Total for ASTX727.
- Total for the AML study.

The number and percentage of subjects experiencing AEs will be summarized by MedDRA SOCs (sorted alphabetically) with PTs sorted alphabetically within each SOC. The number and percentage of subjects experiencing AEs will also be summarized by PT and sorted by event frequency of the Total for ASTX727 column. Related AEs, serious AEs (SAEs), and related SAEs will be summarized similarly. A summary of AEs with fatal outcome, AEs resulting in permanent treatment discontinuation, and AEs resulting in treatment delay or dose reduction will also be provided. Additional summaries will be generated by SOC, PT and CTCAE grade. For these

summaries, if the occurrence of a particular AE for a given subject is reported more than once, the event is only counted once with its worst CTCAE grade.

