### Study Assessments and Procedures:

Study evaluation visits will occur on Days 1-5, then weekly, in Cycles 1 and 2. Bone marrow samples will be collected from subjects at Screening or within 21 days before Cycle 1 Day 1; on or before Day 1 of Cycles 3, 5, and 7, then every 3 months in first year and every 6 months thereafter. A manual differential of the myeloid cells in bone marrow will be performed with a minimum of 100 cells counted and a specific myeloblast percent generated. Complete blood count and differential will be obtained weekly during Cycles 1 and 2 then biweekly in Cycles ≥3, with specific output being hemoglobin, platelet count, white blood cell count and percent neutrophils (percent polymorphonuclear neutrophils and bands) or an absolute neutrophil count, and percentage of blasts. QTc interval will be assessed via routine ECG at Screening and on Day 3 of Cycles 1 and 2. The severity (intensity) of AEs will be graded according to the National Cancer Institute (NCI) Common Terminology Criteria for Adverse Events (CTCAE) for Cancer Clinical Trials, version 4.03.

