## 11.8 Safety Analyses

The Safety Analysis Set will be used for all safety analyses. Safety will be assessed by subject reported and investigator observed AEs, along with concomitant medications, physical examination, clinical laboratory tests (hematology and serum chemistry), vital signs, ECOG performance status and ECG. Safety will also be assessed by exposure to ASTX727 or IV decitabine, reasons for discontinuation, deaths, and causes of deaths.

AEs will be mapped to the appropriate System Organ Class (SOC) and Preferred Term (PT) according to the Medical Dictionary for Regulatory Activities (MedDRA). Severity of AEs will be graded using CTCAE version 4.03 (Appendix 2). All AEs collected during the study will be presented in data listings. Treatment-emergent AEs (TEAEs) are defined as events that first occur or worsen after the subject receives study drug on C1D1 until 30 days after the last dose of study treatment, or the start of an alternative anti-cancer treatment for MDS/CMML or subsequent leukemia, whichever occurs first, to be defined in more detail in the statistical analysis plan. The summary will be provided for all AEs, AEs considered related to study treatment, SAEs and related SAEs as follows based on the treatment period when the events occur:

- By maximum severity.
- Incidence by SOC (by severity grade and overall).
- Incidence rate by PT (by severity grade and overall) within each SOC.

Laboratory values will be graded, if possible, by CTCAE in conjunction with the Harrison (18th edition) laboratory normal reference ranges. Shift tables will be provided for each graded laboratory test.

Concomitant medications are the medications taken with a start date on or after the start of the administration of the study drug (C1D1), or those with a start date before the start of study drug administration (C1D1) and a stop date on or after the start of study drug administration (C1D1), as to be defined in more detail in the statistical analysis plan. Concomitant medication will be coded by the WHO Drug Dictionary and summarized by Therapeutic subgroup (Anatomical Therapeutic Chemical [ATC] level 2) and PT, sorted alphabetically, using counts and percentages.

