## 7.0 STATISTICAL ANALYSIS

Unless otherwise specified, all statistical tests and confidence intervals (CIs) described in this document will be two-sided with alpha = .05. The SAS® statistical package (version 9.4 or a later version) will be used for the analyses.

The first dosing date is defined as the first date the subject received any study treatment. Subject disposition, demographics, and baseline characteristics will be summarized by treatment sequence and all subjects combined (Total). Adverse events (AEs) will be summarized by actual treatment received at the onset of the AE (Section 7.6.2). Efficacy analyses, laboratory tests, vital signs, ECG, and ECOG performance status will be summarized by treatment sequence and all subjects combined (Total), unless otherwise specified.

The following data listings by study center and subject ID will be provided: screened subjects (with reason for screen failure), disposition (with reasons for discontinuation of treatment and withdrawal from study), important protocol deviations, demographic and baseline characteristics, study drug administration, individual efficacy data, subjects excluded from the efficacy analysis, AEs, all deaths (including primary cause of death), serious adverse events (SAEs), other significant AEs (including treatment discontinuation due to AEs), concomitant medications, and the protocol specified laboratory measurements. Additional data listings may be generated to support other relevant discussions in Clinical Study Report.

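### SAP 7.6.2 gives AEs only as crude subject percentages, so the Cycle 3 or later and Total for ASTX727 columns cannot be read against the one-cycle columns

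*SAP*

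**What the plan says.** SAP 7.6.2 (Adverse Events) sets the layout: "All summaries of AEs will be made separately in the following groups". Five groups follow: IV decitabine in Cycle 1 or 2, ASTX727 in Cycle 1 or 2, ASTX727 in Cycle 3 or later, Total for ASTX727, and the total for the AML study. SAP 7.0 gives the attribution rule: "Adverse events (AEs) will be summarized by actual treatment received at the onset of the AE".

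The measure is a crude proportion: "The number and percentage of subjects experiencing AEs will be summarized by MedDRA SOCs". In the summaries by class, term and grade, "the event is only counted once with its worst CTCAE grade". The preferred-term table is "sorted by event frequency of the Total for ASTX727 column", so these groups are columns of one table and that total sets the row order.

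Under SAP 3.1 each subject receives one cycle of each product in Cycles 1–2, then ASTX727 in 28-day cycles until progression, unacceptable toxicity or the subject's decision to stop. SAP 7.6.1 describes cycles per subject but does not link them to AEs. Nowhere does the SAP give a rate per cycle or per unit of time, a denominator for each column, or a caution about reading across columns.

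Protocol 11.8 also groups AEs "based on the treatment period when the events occur" and mentions an incidence rate by preferred term without a time denominator. SAP 1.0 says that the SAP supersedes the protocol's analysis plan for the AML subjects.

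**The concern.** A subject counts once however often an event recurs, so extra time in a column can raise the percentage and never lower it. The IV column holds one cycle per subject. The Cycle 3 or later and Total for ASTX727 columns hold as many cycles as the subject stays on treatment. Two products with the same toxicity per cycle would therefore show different percentages.

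Long-term safety of ASTX727 is a secondary objective (SAP 2.2), and SAP 6.0 describes the analysis as being for submission. A reader who sets the total column beside IV decitabine would see an apparent excess on ASTX727 that may only reflect longer treatment. A reader who sets early beside later ASTX727 cycles would see an apparent rise with time on drug for the same reason.

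**Working it through.** The documents state no AE figure, so there is none to reproduce. The check asks what the planned columns would show if nothing differed except the number of cycles.

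**Inputs**
- Cycles per column (SAP 3.1): IV, 1; ASTX727 in Cycle 1 or 2, 1; Cycle 3 or later, k; Total for ASTX727, k + 1.
- k = 4 (assumption, guided by SAP 6.0). The analysis follows 6 months of follow-up or earlier discontinuation. Taking 6 months as 182 days, 182/28 = 6.5 cycles. A subject still on treatment has 6.5 − 2 = 4.5 cycles after Cycle 2, of which 4 are complete.
- p, the risk of a first event per cycle: assumed the same in every column, constant and independent between cycles. Range shown: 5% to 20%.

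**Crude percentage over c cycles = 1 − (1 − p)^c**

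| p | IV, c = 1 | ASTX727 Cycle 1 or 2, c = 1 | Cycle 3 or later, c = 4 | Total for ASTX727, c = 5 |
|---|---|---|---|---|
| 5% | 5% | 5% | 1 − 0.95^4 = 18.5% | 1 − 0.95^5 = 22.6% |
| 10% | 10% | 10% | 1 − 0.90^4 = 34.4% | 1 − 0.90^5 = 41.0% |
| 20% | 20% | 20% | 1 − 0.80^4 = 59.0% | 1 − 0.80^5 = 67.2% |

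With only 2 later cycles and p = 10%, Cycle 3 or later shows 19.0% and Total for ASTX727 27.1%.

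**Allowing for discontinuation.** Assume 5%, 12% or 20% of subjects stop after each cycle, a cap of 7 cycles in all, half the subjects in each sequence, and p = 10%. Worked for 20%: the shares of subjects with 1, 2, 3, 4, 5 and 6 ASTX727 cycles are 0.260, 0.128, 0.102, 0.082, 0.066 and 0.262. They sum to 0.900; the other 0.100 stop after an IV first cycle. Weighting 1 − 0.9^c by these shares gives 0.256, and 0.256/0.900 = 28.4%. At 12% and 5% discontinuation the result is 34.5% and 41.2%. The Cycle 3 or later column runs from 29% to 38%. IV stays at 10%.

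**Denominator.** At 20% discontinuation, 64% of subjects reach Cycle 3. The Cycle 3 or later entry is 28.8% of subjects dosed in that column, but 0.288 × 0.64 = 18.4% of all treated subjects. The SAP does not say which applies.

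**Which rate removes the artefact** (p = 10%, 5 ASTX727 cycles)
- Cycles at risk up to and including the first event, per subject: 1 + 0.9 + 0.81 + 0.729 + 0.6561 = 4.095. Rate: 0.4095/4.095 = 10.0 per 100 cycles, the same as IV (0.10/1).
- All treated cycles: 0.4095/5 = 8.2 per 100 cycles against 10.0 for IV. This over-corrects and makes ASTX727 look safer.

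**Ascertainment.** In the supplied US protocol, visits in the first two cycles are frequent ("Study evaluation visits will occur on Days 1-5, then weekly, in Cycles 1 and 2"), giving AE recording on Days 1–5, 8, 15 and 22: 8 per cycle. In Cycles ≥3, Table 9 marks Day 1 only. Its hematology footnote reads "Collect weekly through Cycle 2, at Days 1 and 15 in Cycles ≥3, and at treatment discontinuation", so 4 counts per cycle become 2. This would push the later column down. If detection there were halved (assumption), p = 10% and k = 4 would show 1 − 0.95^4 = 18.5% instead of 34.4%.

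**The case against.** The best defence is that the SAP already holds a fair comparison. IV decitabine and ASTX727 in Cycle 1 or 2 are one cycle each, in randomized order and on the same visit schedule. No test or contrast between AE columns is planned, and sorting on a column only orders rows. Exposure is tabulated, columns are labelled by cycle, and a cumulative percentage is an ordinary summary for long-term safety. All of this stands. It makes this a matter of interpretation, not a testing error. It does not supply a rate for the columns that span more cycles, and the SAP does not say which pair is the product comparison.

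Three stronger readings are tempting, and the documents do not support them.

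- A reader might infer that the product contrast cannot be read at all. The two Cycle 1–2 columns answer that.
- A reader might extend the arithmetic to 11 ASTX727 cycles, where a 10% risk gives 69%. That needs 11 cycles without dropout, a duration that nothing in the documents supports for these subjects.
- A reader might conclude that sparser blood counts halve the detection of cytopenias. With onset uniform over the cycle, a 7-day episode is caught by 100% of weekly and 50% of two-weekly schedules, but that is illustrative only. Protocol 7.6 expects the maximal drug effect on Day 15, which stays on the later schedule. The Table 9 footnotes have AEs collected throughout the study, and SAP Appendix 1 (Appendix D, rule 4) has sites queried for missing weekly counts, although for dating responses. The schedule itself comes from the US MDS/CMML protocol, whereas this SAP covers AML subjects under a European amendment (SAP 1.0) that was not supplied.

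**Conclusion.** The point holds for the columns with unequal time at risk. From crude percentages one cannot read Total for ASTX727 against IV decitabine, or early against later ASTX727 cycles. Equal assumed risk per cycle over 5 ASTX727 cycles produces 10% against 41%, or 5% against 23%. Discontinuation of 5–20% per cycle leaves the total at about 28–41% against 10%.

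The direction follows from the SAP alone. The size rests on assumed values for risk per cycle, number of cycles and dropout, and on constant, independent risk. The ascertainment effect would act the other way in the later column, but it is conditional on the AML schedule and its size is unknown. A rate would not remove it, nor the selection of subjects who stay on treatment into Cycle 3.

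This is a cheap improvement to descriptive tables that serve a stated secondary objective. It does not extend to Protocol 11.8: the MDS/CMML subjects have a separate SAP, not supplied, which may already deal with it.

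**What to change.** In SAP 7.6.2:

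1. Name the two Cycle 1–2 columns as the IV versus oral comparison.
2. For each column, state the denominator (subjects dosed in that column) and add an exposure-adjusted incidence rate. Define it as subjects with a first event in that column, divided by the cycles or subject-months at risk in that column up to and including that first event. Do not divide by all treated cycles. Derive it from dosing and AE dates; the cycle counts of SAP 7.6.1 do not stop at the first event.
3. Footnote that Cycle 3 or later and Total for ASTX727 cover more cycles than IV decitabine and are not compared with it on crude percentages.
4. If the AML regional protocol also reduces visits and blood counts from Cycle 3, say so in a footnote. A cytopenia table restricted to Day 1 and Day 15 counts in all cycles is optional.

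The cost is SAP wording, one extra rate per column and some programming. No new data or procedures are needed. The downside is longer tables.
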